Routine monitoring of cyclosporine blood levels is an important safety measure. For monitoring cyclosporine levels in whole blood, a specific monoclonal antibody (measurement of parent drug) is preferred. A high performance liquid chromatography method, which also measures the parent drug, can be used as well. If plasma or serum is used, a standard separation protocol (time and temperature) should be followed. It must be remembered that cyclosporine concentration in blood, plasma or serum is only one of many factors contributing to the clinical status of the patient. Results should serve only as a guide to dosage in relationship to other clinical and laboratory parameters.

Live-attenuated vaccines

During treatment with cyclosporine, vaccination may be less effective. The use of live-attenuated vaccines should be avoided.

Pregnancy

Animal studies have shown reproductive toxicity in rats and rabbits.

Breast-feeding

Cyclosporine passes into breast milk. The ethanol content of the cyclosporine formulations should also be taken into account in women who are breast-feeding.

Others

Other potential side effects on cyclosporine included: hypertension, blood lipids increases, hyperkalemia, hypomagnesemia, hyperuricemia, infections, acute and chronic nephrotoxicity.

Refer to the label for additional information regarding the safety profile and potential interactions with cyclosporine.

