6.3.1.3 Cyclosporine dose modification due to increase in blood pressure

Cyclosporine can cause blood pressure increase. After informed consent is obtained follow [Table 7-1](#) and [Section 7.2.2.2](#) for regular blood pressure monitoring guidelines.

If there is an increase in blood pressure, treatment with an appropriate antihypertensive agent must be initiated. Preference must be given to an antihypertensive agent that does not interfere with the pharmacokinetics of cyclosporine.

Potassium-sparing drugs must not be used as hyperkalemia can occur. If there is no improvement in blood pressure, cyclosporine dose must be decreased by 25% to 50%. Cyclosporine must be discontinued if antihypertensive treatment(s) and dose decreases do not result in return to baseline blood pressure.

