6.3.1.4 Cyclosporine dose modification due to nephrotoxicity

After informed consent is obtained follow [Table 7-1](#) and [Section 7.2.2.5](#) for regular serum creatinine and BUN monitoring. Cyclosporine can cause nephrotoxicity.

The cyclosporine induced nephrotoxicity is usually associated with elevation of serum creatinine and blood urea nitrogen (BUN) levels. These changes are usually dependent on the cyclosporine dose and initially reversible with a dose reduction. In general, fine-tuning of the cyclosporine dose to the lower end of the therapeutic range, adequate hydration, optimization of blood pressure control, and avoidance of other nephrotoxic agents, can improve the safety and tolerability.

A peripheral blood smear evaluation is recommended to rule out hemolytic uremic syndrome.

If the serum creatinine is greater than or equal to 25% above the patient's pre-treatment level, serum creatinine must be repeated within two weeks. In the interim, increase of fluid intake and decrease dose of other concomitant nephrotoxic medications (e.g., antibiotics) is recommended.

If the change in serum creatinine remains greater than or equal to 25% above baseline, Cyclosporine may be reduced by 25% to 50%. If at any time the serum creatinine increases by greater than or equal to 50% above pretreatment level, the cyclosporine must be reduced by 25% to 50%. Cyclosporine must be discontinued if reversibility (within 25% of baseline) of serum creatinine is not achievable after two dose modifications.

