7.2.2.5 Laboratory evaluations

Clinical laboratory analyses managed by central laboratory are detailed in the [Table 7-3](#) for the first 6 months only. All other analysis required in the VES for first 6 months and analysis done during the additional 18 months follow-up (responders only) as per standard of care will be managed by local laboratory and are detailed in [Table 7-4](#) and [Table 7-5](#).

At any time during the study, abnormal laboratory parameters which are clinically significant and require an action to be taken with study treatment (e.g., require dose modification and/or interruption of study treatment, lead to clinical symptoms or signs, or require therapeutic intervention), whether specifically requested in the protocol or not, will be recorded on the AE eCRF page.

A central laboratory will be used for analysis of listed specimens collected in the first 6 months of the study. Details on the collections, shipment of samples and reporting of results by the central laboratory are provided to investigators in the laboratory manual.

Table 7-3 Clinical laboratory parameters collection plan for central lab (first 6 months)

Test Category	Test Name
Hematology	Hematocrit, Hemoglobin, MCH, MCHC, MCV, Platelets, Red blood cells, White blood cells, RBC Morphology, Differential (absolute and percentages)(Basophils, Eosinophils, Lymphocytes, Monocytes, Neutrophils and Other), Reticulocytes, and a Peripheral blood smear
Folate/B12 panel	Serum folate, Vitamin B12 (cobalamin)
Viral serologies included Hepatitis markers	Hepatitis A, B, C, human immunodeficiency virus (HIV), Herpes simplex virus (HSV), Epstein Barr virus (EBV), and cytomegalovirus (CMV) HBV-DNA, HbsAg, HbsAb, HbcAb, HCV RNA-PCR (baseline)
Chemistry	Albumin, Alkaline phosphatase, ALT, AST, Gamma-glutamyl-transferase (GGT), Lactate dehydrogenase (LDH), Bicarbonate, Calcium, Magnesium, Phosphorus, Chloride, Sodium, Potassium, Creatinine, Creatine kinase, Direct Bilirubin, Indirect Bilirubin, Total Bilirubin, Total Cholesterol, LDL, HDL, Total Protein, Triglycerides, Blood Urea Nitrogen (BUN) or Urea, Uric Acid Amylase, Lipase, Glucose (fasting)
Urinalysis	Microscopic Panel (Red Blood Cells, White Blood Cells, Casts, Crystals, Bacteria, Epithelial cells) Macroscopic Panel (Color, Bilirubin, Blood, Glucose, Ketones, Leukocytes esterase, Nitrite, pH, Protein, Specific Gravity, Urobilinogen)

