10.5.3.3 Laboratory abnormalities

Grading of laboratory values will be assigned programmatically as per NCI Common Terminology Criteria for Adverse Events (CTCAE) version 4.03. The calculation of CTCAE grades will be based on the observed laboratory values only, clinical assessments will not be taken into account.

CTCAE Grade 0 will be assigned for all non-missing values not graded as 1 or higher. Grade 5 will not be used.

For laboratory tests where grades are not defined by CTCAE version 4.03, results will be categorized as low/normal/high based on laboratory normal ranges.

The following summaries will be generated separately for key hematology and biochemistry tests laboratory tests:

- Worst post-baseline CTCAE grade (regardless of the baseline status). Each patient will be counted only once for the worst grade observed post-baseline.
- Shift tables using CTCAE version 4.03 grades to compare baseline to the worst on-treatment value
- For laboratory tests where grades are not defined by CTCAE version 4.03, shift tables using the low/normal/high/ (low and high) classification to compare baseline to the worst on-treatment value.

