2.7.3 Laboratory data

Laboratory values (central and local) are converted to the international system of units (SI). CTCAE Grade 0 will be assigned for all non-missing values not graded as 1 or higher. Grade 5 will not be used. For laboratory tests where grades are not defined by CTCAE version 4.03, results will be categorized as low/normal/high based on laboratory normal ranges.

The following summaries will be generated separately for hematology and for the safety set:

- Shift tables by CTCAE grade (or low/normal/high classification) to compare baseline to the worst on-treatment value:
 - Hematology: Neutrophils (absolute), platelets and hemoglobin
 - Chemistry: Creatinine, total bilirubin (TBL), aspartate aminotransferase (AST), alanine aminotransferase (ALT) and alkaline phosphatase (ALP)
- Summary statistics on platelets for change from baseline for months 3, 6, 12 and 24 will be provided. On-treatment platelet values will be used up to Month 24.
- Box plots showing parameter values over time (baseline and on-treatment time points 3, 6, 12 and 24 months) will be displayed based on time windows for the following selected parameters: Neutrophils (absolute), platelets, reticulocytes, hemoglobin and RBCs. Boxplots will display boxes (25th – 75th percentiles) and median (line) as well as joint mean (dot) values. Whiskers extend to the 10th – 90th percentiles with any values outside the whiskers not being displayed. A footnote will explain that these values are not displayed. However, all values are used to calculate mean and percentiles displayed on the graph. The number of observations used for this analysis is to be stated at the bottom.

Listings of laboratory data (hematology and biochemistry) will be provided showing the corresponding CTCAE grades, if applicable, and the classifications relative to the laboratory normal ranges. Values measured outside of on-treatment period will be flagged.

Liver function parameters

Liver function parameters of interest are TBL, ALT, AST and ALP.

The number (%) of patients with worst on-treatment values will be summarised:

- ALT or AST > 3xULN
- ALT or AST > 5xULN
- ALT or AST > 8xULN
- ALT or AST > 10xULN
- ALT or AST > 20xULN
- TBL > 2xULN
- TBL > 3xULN
- ALT or AST > 3xULN & TBL > 2xULN
- ALT or AST > 3xULN & TBL > 2xULN & ALP \geq 2xULN
- ALT or AST > 3xULN & TBL > 2xULN & ALP < 2xULN (potential Hy's law)

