2.7.4.2 Vital signs

Vital sign assessments are performed in order to characterise basic body function. The following parameters were collected: height (cm, inch), weight (kg, pound), body temperature (°C, Fahrenheit), position, pulse (beats/minute), systolic and diastolic blood pressure (mmHg).

The number (%) of patients with notable values will be presented.

Table 2-4 Notable criteria for vital signs

Vital sign (unit)	Notable low value	Notable high value
Weight (kg)	decrease \geq 10% from baseline	increase \geq 10% from baseline
Body temperature (°C)	--	\geq 39.1
Pulse rate (bpm)	\leq 50 and decrease from baseline of $>25\%$	\geq 100 and increase from baseline of $>25\%$
Systolic blood pressure (mmHg)	\leq 90 and decrease from baseline of ≥ 20	\geq 180 and increase from baseline of ≥ 20
Diastolic blood pressure (mmHg)	\leq 50 and decrease from baseline of ≥ 15	\geq 105 and increase from baseline of ≥ 15

A listing of all vital sign assessments will be produced and notable values will be flagged. Assessments collected outside of on-treatment period will be flagged.

ECOG performance status

The eastern cooperative oncology group (ECOG) performance status will be used to assess physical health of patients, ranging from 0 (most active) to 5 (least active).

Shift tables comparing the baseline status with the worst post-baseline status will be provided.

Table 2-5 ECOG performance scale

Score	Description
0	Fully active, able to carry on all pre-disease performance without restriction
1	Restricted in physically strenuous activity but ambulatory and able to carry out work of a light or sedentary nature, e.g., light house work, office work
2	Ambulatory and capable of all self-care but unable to carry out any work activities. Up and about more than 50% of waking hours
3	Capable of only limited self-care, confined to bed or chair more than 50% of waking hours
4	Completely disabled. Cannot carry on any self-care. Totally confined to bed or chair
5	Dead

A listing of all ECOG performance status assessments will be produced, flagging assessments collected outside of the on-treatment period.

Ophthalmic and neurologic examinations

No summaries or listings as only collected as source data.

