3.1.1 Bayesian calculus for a binary endpoint

For the binary endpoint ORR, let Y be the number of responders in n subjects. The sampling model is binomial

$$Y | \theta \sim \text{Bin}(n, \theta)$$

with true response rate θ . The prior distribution is a Beta distribution

$$\theta \sim \text{Beta}(a, b)$$

In this conjugate setting, the posterior distribution is again a Beta distribution

$$\theta | Y \sim \text{Beta}(a+Y, b+n-Y)$$

Here, the parameters a and b are the a priori number of responders and non-responders, respectively, and $a+b$ is the prior effective sample size.

For this study, the parameters (a, b) of the Beta prior distribution are $a = 0.25$ and $b = 1$. This prior distribution has mean = $a / (a + b) = 0.25 / (0.25 + 1) = 0.2$ assuming a low response rate a priori. Furthermore, the prior effective sample size is small ($a + b = 1.25$).

4 Changes to protocol specified analyses

Supportive efficacy analyses were added as specified in [Section 2.5.2](#).

Not all laboratory and liver event data will be listed, listings for key biochemistry, hematology and hepatic parameters will be provided.

Sample size characteristics were added based on the enrollment of 54 patients.

Age categories is changed to <60, >=60. Additional subgroups analysis by age, ethnicity and/or responder status were added for demographic characteristics, overall hematological response, transfusion information and relevant AEs.

Boxplots displaying parameter values over time for the patient-reported outcomes were added.

5 References

1. Brookmeyer R and Crowley J (1982). A Confidence Interval for the Median Survival Time. *Biometrics*, 38, 29 - 41.
2. Clopper CJ and Pearson ES (1934). The use of confidence or fiducial limits illustrated in the case of the binomial. *Biometrical*, 26, 404-413.
3. Collet D (1994). Modelling survival data in medical research. London, Chapman & Hall.
[REDACTED]
4. [REDACTED]
5. Neuenschwander B, Branson M and Gsponer T (2008). Critical aspects of the Bayesian approach to Phase I cancer trials. *Statistics in Medicine*, 27, 2420-2439.
6. Oncology guideline for safety analysis, v1.0, dated 09-Jun-2016
7. Spiegelhalter DJ, Abrams KR and Myles JP (2004). Bayesian Approaches to Clinical Trials and Health-care Evaluation. Chichester, Wiley.

6 Appendix 1

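### For potassium, magnesium, uric acid, lipids and blood-pressure rises below 180/105 mmHg, the SAP's summary tables depend entirely on investigator-reported adverse events

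*Protocol*

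**What the plan says.** **Known effects.** Protocol 1.2.2.2.1 lists for cyclosporine: "Other potential side effects on cyclosporine included: hypertension, blood lipids increases, hyperkalemia, hypomagnesemia, hyperuricemia, infections, acute and chronic nephrotoxicity". The same section places hypertension and renal dysfunction among the principal adverse reactions.

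**Objective.** Objective 9 (protocol Table 3-1, SAP Table 1-1) is the safety of the combination and includes evaluating changes in laboratory values.

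**Collection.** The central chemistry panel for the first 6 months (protocol Table 7-3) includes "Calcium, Magnesium, Phosphorus, Chloride, Sodium, Potassium, Creatinine, Creatine kinase, Direct Bilirubin, Indirect Bilirubin, Total Bilirubin, Total Cholesterol, LDL, HDL, Total Protein, Triglycerides", with BUN and uric acid in the same row. Protocol 7.2.2.5.2 has chemistry run centrally at every visit in that period.

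**Planned laboratory summaries.** Protocol 10.5.3.3 reads: "The following summaries will be generated separately for key hematology and biochemistry tests laboratory tests". It does not name the key tests. SAP 2.7.3 does so for the shift tables: "Chemistry: Creatinine, total bilirubin (TBL), aspartate aminotransferase (AST), alanine aminotransferase (ALT) and alkaline phosphatase (ALP". On listings, SAP section 4 states: "Not all laboratory and liver event data will be listed, listings for key biochemistry, hematology and hepatic parameters will be provided". It does not name the key parameters.

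**Blood pressure.** SAP Table 2-4 counts a high systolic value only if it is ≥180 mmHg and has risen by ≥20 from baseline, and a high diastolic value only if it is ≥105 mmHg and has risen by ≥15. All vital-sign values are listed. Protocol 10.5.3.4 says vital-sign data will be tabulated and listed, and that counts of notable values will be given in addition.

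**The concern.** The combination under study contains cyclosporine, and the protocol names its metabolic, electrolyte and blood-pressure effects. Apart from creatinine, the SAP's tables of measured chemistry values concern the liver: bilirubin, AST, ALT and ALP have shift tables, and a further set of ten threshold rows covers liver function. Adverse events of special interest are defined as specific to eltrombopag (SAP 2.7.1), so they do not target the cyclosporine effects either.

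The trial is open-label with a single arm. Whether a modest rise in potassium or blood pressure is recorded as an adverse event rests largely on the investigator's judgment of clinical significance. Measured values are the natural check on that reporting. For these parameters the plan leaves the check out of its summary tables.

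**Working it through.** No power or error-rate calculation applies. The check sets the protocol beside the SAP and then works through the blood-pressure rule.

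**1. Named effect against SAP output**

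| Effect (protocol 1.2.2.2.1) | Measured | SAP summary of measured values | Other SAP output |
|---|---|---|---|
| Hyperkalemia | Potassium | None | AE tables |
| Hypomagnesemia | Magnesium | None | AE tables |
| Hyperuricemia | Uric acid | None | AE tables |
| Lipid increases | Cholesterol, LDL, HDL, triglycerides | None | AE tables |
| Nephrotoxicity | Creatinine, BUN | Creatinine shift table | AE tables |
| Hypertension | Blood pressure | Count at ≥180 or ≥105 with the required rise | AE tables, full listing |

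Four of the six rows have no summary of measured values. The box plots in SAP 2.7.3 cover blood counts only. Infections, the remaining named effect, are an adverse-event matter and not in question.

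**2. What reaches the AE tables.** Under protocol 8.1.1, an abnormal laboratory value or test result is an adverse event if it causes signs or symptoms, is considered clinically significant, requires therapy, or requires a change in study medication. Protocol 8.1.2.1 repeats this, and 7.2.2.5 sends clinically significant values needing action on study treatment to the AE page. What is left out is a change that meets none of the four conditions.

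**3. The blood-pressure rule.** Because the level and the rise must both be met, the rise needed to be counted is:

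- systolic: max(20, 180 − baseline)
- diastolic: max(15, 105 − baseline)

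| Assumed baseline (mmHg) | Systolic rise needed | Diastolic rise needed |
|---|---|---|
| 120/75 | max(20, 60) = 60 | max(15, 30) = 30 |
| 140/80 | max(20, 40) = 40 | max(15, 25) = 25 |
| 160/90 | max(20, 20) = 20 | max(15, 15) = 15 |

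Below a baseline of 160 systolic or 90 diastolic, the absolute level decides and the SAP's own increments of 20 and 15 have no effect. A patient moving from 120/75 to 165/100 has risen by 165 − 120 = 45 systolic and 100 − 75 = 25 diastolic, and is not counted. Above 160 the increment decides: 165 to 180 is a rise of 15, also not counted.

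**4. Vital signs, protocol against SAP.** Protocol 10.5.3.4 promises a tabulation, a listing and notable-value counts. SAP 2.7.4.2 has the counts and the listing. SAP section 4 does not mention the missing tabulation.

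**5. Data available.** Protocol Table 7-1 schedules Weeks 1 to 8 (8 visits) and Weeks 10, 12, …, 26 (9 visits), so 17 visits, of which 16 follow Day 1. For five analytes (potassium, magnesium, uric acid, total cholesterol, triglycerides) that is at most 16 × 5 = 80 post-baseline central results per patient. This shows that the data exist; it does not measure harm.

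**The case against.** The other side has a strong case, and much of it stands.

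- **Acted-on toxicity is captured.** A reader might infer that patients could have cyclosporine reduced or stopped for these toxicities while the report shows nothing. The documents do not support that. A change in study medication makes the abnormality an adverse event (protocol 8.1.1, 8.1.2.1). SAP 2.7.1 tabulates all on-treatment AEs by preferred term and separately those leading to adjustment, interruption or discontinuation. SAP 2.4.1 gives dose changes with reasons for each drug. For raised pressure, protocol 6.3.1.3 states: "If there is an increase in blood pressure, treatment with an appropriate antihypertensive agent must be initiated". Drugs started that way enter the concomitant-medication summary (SAP 2.4.2).
- **Nephrotoxicity is tabulated.** Creatinine has a baseline-to-worst shift table. Protocol 6.3.1.4 works with relative rises ("If the change in serum creatinine remains greater than or equal to 25% above baseline"), but that is a dose-management trigger for one patient, and nothing makes it a reporting cut-off.
- **No direct contradiction on chemistry.** The protocol promises summaries of unnamed key tests, so the short list is unexplained rather than inconsistent. The protocol's separate worst-grade summary is also absent from SAP 2.7.3, but the margins of the shift tables give much the same information for the tests they cover.
- **Listings.** The narrowing is declared in SAP section 4, and nothing shows that potassium or magnesium falls outside the key parameters. Every blood-pressure value is listed.
- **QTcF.** It is tempting to argue that these tables are needed to interpret QTcF prolongation. Protocol 6.3.2 has electrolytes checked in the affected patient at the time; a worst-value shift table is not time-matched to the ECG and would not serve that purpose.

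This does not answer the residual point. Changes outside the four AE conditions have no summary, and the vital-sign tabulation has gone without being declared.

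**Conclusion.** The point holds in a limited form. For potassium, magnesium, uric acid and lipids, and for blood-pressure rises short of the 180/105 mmHg rule, the SAP's summary tables show a change only if an investigator recorded it as an adverse event. Measured changes that were asymptomatic, not judged clinically significant, untreated and without effect on study medication appear in no summary table. The protocol nevertheless names these effects, collects the data and makes laboratory change part of objective 9. The dropped vital-sign tabulation is a small, undeclared departure from the protocol.

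It would go too far to conclude that the safety tables cannot show cyclosporine toxicity, or that the report would cover little beyond the liver. The SAP also provides full AE tables, shifts in blood counts and creatinine, ECG, vital-sign counts and deaths.

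How many patients fall in the gap cannot be derived from the documents. The blood-pressure figures rest on assumed baselines; the rule applied to them is the SAP's. The case for change is that it is cheap and reduces dependence on AE reporting in an uncontrolled, open-label study.

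**What to change.** For the final analysis:

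- **SAP 2.7.3.** Add potassium (high and low), magnesium (low), uric acid, total cholesterol and triglycerides to the baseline-to-worst shift tables, by CTCAE grade or the SAP's existing low/normal/high classification. Limit these tables to the central-laboratory data of the first 6 months, or show that period separately. Later chemistry is local, protocol Table 7-5 describes it as only potentially collected, and protocol 7.2.2.5.1 makes only the four efficacy parameters a reporting minimum.
- **SAP 2.7.4.2.** Restore the vital-sign tabulation with a change-from-baseline summary of systolic and diastolic pressure. Add a row counting a rise ≥20 systolic or ≥15 diastolic without the 180/105 condition. These are the SAP's own increments, used for reporting and not as a treatment threshold. Keep the existing rows.
- **Optional.** Rows for creatinine ≥25% and ≥50% above baseline.

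The cost is SAP wording and a few more tables from data already collected. The additions can enter only the final report, because the SAP introduction records that the primary report has been written.
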